 This subject group may require immediate escalation of care and/or hospitalization once the digital monitoring system identifies changes.

Design

During screening, subjects and caregivers will be trained on the CWHMS and assessed for compliance (Table 1-1, panel 1). **Once enrolled,** subjects will receive 2 **complete** cycles of blinatumomab in the outpatient setting in accordance with the monitoring and intervention guidelines (Table 1-1., panels 2 and 3).

After the end of cycle 2 clinical assessment visit, some subjects may continue to receive 2 additional (optional) cycles of **outpatient** blinatumomab. There will be no CWHMS outpatient monitoring during the optional cycles 3 and 4. For the purpose of this study, the MDMP is defined as the first 3 days of cycle 1 (72 hours) and the first 2 days of cycle 2 (48 hours) of blinatumomab infusion for subjects with MRD of B-precursor ALL.

The end of study visit will occur 30 days (+ 3 days) after the last dose of blinatumomab is administered (Figure 1-1).

During the MDMP, the CWHMS will measure vital signs. These vital signs include **pulse** rate, **respiratory rate**, oxygen saturation, **and axillary temperature**. The CWHMS will measure respiratory rate intermittently (sampling every 30 seconds). The subjects will

Date: 21 April 2022 Page 12 of 108

Product: Blinatumomab
Protocol Number: 20190014

take intermittent blood pressure (BP) measurements (using a subject-usable BP device) every 3 hours during the MDMP. The schedule for BP measurements may be extended by HCP (up to but not exceeding every 6 hours) after the first 24 hours of MDMP. The BP device will be provided and will directly transmit the BP reading via the monitoring platform to the **CH Patients Application on the study provisioned mobile phone**.

Threshold vital sign values will be established, and an immediate alert will be generated and transmitted to the **monitoring platform** once the preset threshold values are surpassed and sustained for at least 10 minutes (Table 1-1). **Except for blood pressure**, an alert will be triggered within 1 minute upon being received.

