In addition, subject and caregiver will be trained on the usual side effects of blinatumomab infusion (fever, erythematous skin rash, chills, confusion, headache, tremor, myalgia, lethargy, somnolence, seizure), and have direct (phone and video) contact with HCP or emergency services if any expected or unexpected side effects occur. The caregiver is expected to be a spouse or close relative such as a child but can be any adult (≥ 18 years) willing and able to participate in the subject's care. The caregiver will remain in the home with the subject for the entire MDMP. The caregiver will be trained to use and have access to the tablet for communication with the HCP, if necessary.

The HCP and the staff will also be trained on the infusion, usual side effects and response algorithm (Table 1-1). The HCP will be **trained** in the treatment of patients with ALL and the use of blinatumomab. The HCP will carry the **study provisioned mobile phone** at all times during the MDMP. The **study provisioned mobile phone** will have cellular connection to the subject's tablet and the CWHMS and will receive vital signs refreshed every 30 seconds for the entire MDMP. Blood pressure will be performed manually by the subject (or caregiver) every 3 hours and the result electronically delivered to the **study provisioned mobile phone**. In addition to the continuous feed of vital signs, an audible alarm will sound every time the vital signs exceed the preset threshold and is consistent for at least 10 minutes. In addition, an audible alarm will sound if there is no data transfer for 15 minutes.

It is not intended that the CWHMS will allow the HCP to identify patients experiencing neurotoxicity. The CWHMS is intended to provide remote monitoring of vital signs. Knowing a subject's vital signs will give the HCP an overall picture of the subject's disposition. In addition to vital signs monitoring, the CWHMS includes the functionality for video calling between the **HCP** and the subject. This allows the HCP to visually

Date: 21 April 2022 Page 13 of 108

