Participants in this clinical investigation shall be referred to as "subjects." Approximately 45 subjects will participate in this study. Refer to Section 9.2 for sample size considerations.

Summary of Subject Eligibility Criteria

Adult subjects with B-cell precursor (BCP) ALL with minimal/measurable residual disease (MRD) defined as a bone marrow (BM) blast count < 5%.

For a full list of eligibility criteria, please refer to Section 5.1 to Section 5.2.

Treatments

Investigational Product

Amgen Investigational Product Dosage and Administration: Blinatumomab is administered as a CiVI.

A single cycle of blinatumomab treatment is 6 weeks in duration, which includes 4 weeks of blinatumomab CiVI followed by a 2-week treatment-free interval. The treatment-free interval may be prolonged by up to 7 days, if deemed necessary by the investigator. For subjects \geq 45 kg, blinatumomab will be administered at a dose of 28 μ g/day for all 4 weeks of continuous treatment. Subjects < 45 kg will be administered blinatumomab 15 μ g/m²/day (max 28 μ g/day).

Date: 21 April 2022 Page 16 of 108

Non-investigational Product

Non-Amgen Non-investigational Product Dosage and Administration:

Dexamethasone

Premedication with dexamethasone (or prednisone): Dexamethasone 16 mg (or equivalent prednisone 100mg) intravenously (IV): up to 6 hours before start of treatment in each treatment cycle. Subjects ≥ 45 kg will have 2 additional 8 mg doses (subjects < 45 kg will receive 2 doses of 5 mg/m² rounded to the nearest mg) of oral dexamethasone to use as needed for treatment of CRS symptoms only if instructed by HCP. It will be recommended that hospitalization be strongly considered for subjects who require interruption of blinatumomab for > 4 hours.

Procedures

Written informed consent must be obtained from all subjects before any study-specific screening procedures are performed. Study-specific procedures will occur according to the Schedule of Assessments (Table 1-2)

For a full list of study procedures, including the timing of each procedure, please refer to Section 8.2 and the Schedule of Activities in Table 1-2.

Statistical Considerations Sample Size Considerations:

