^c End of Study to be conducted 30 (+3 days) after last dose of blinatumomab

All MRD assessments per institutional standard of care procedures. No central MRD testing will be required Subjects can be transplanted at any time according to institutional guidelines and Standard of Care.

Date: 21 April 2022 Page 19 of 108

Table 1-1. Vital Signs and Clinical Monitoring

AMG 103 20190014 VS and Clinical Monitoring

Panel 1

Education

- HCP, Subjects & Caregivers (CG)
 will receive training in the use
 and functions of the Current
 Health (CH) monitoring
 device(s)(CHDs), including the
 temperature sensor, BP monitor,
 and tablet
- Subject will wear CHDs during screening to establish baseline VS, comfort, and eligibility.
- Subject and CG will be trained to recognize clinical changes/symptoms such as increased lethargy, change in mental status, seizure, jitteriness, fever, fast or difficult breathing and other signs and symptoms
- Subject and CG will be educated on the usual side effects of blinatumomab (IP) infusion.
- Subject and CG will be educated to contact HCP for any change or new finding
- HCPs will be trained on outpatient IP infusion and response algorithm

Panel 2

Monitoring

Electronic monitoring including

- Establishment of Subject baseline during screening
- Remote monitoring of vital signs (VS): Respiratory rate (RR), Pulse rate (PR), temperature(T), Blood Pressure(BP), Oxygen saturation(S).
- Monitoring: Continuous PR, T, and S. intermittent: RR(every 30 secs) and BP(every 3 hrs.)
- HCP may order more frequent VS as needed.
- VS algorithm for ALERT to changes in VS as outlined, which are persistent for ≥ 10 minutes, with the exception of BP, alert will occur within 1 minute of measurement:
 - Systolic BP ≤ 100 mmHg or ≥ 20% reduction from baseline (established in screening)
 - Temp ≥ 38.0°C(100.4°F) (Axillary fever scout ≥37.0°C) (99.4°F))
 - S ≤ 92%
 - $R \le 10 \text{ or } \ge 25$
 - PR \leq 60 or \geq 150
- Neurological algorithm for intervention
 - Any seizure
 - Aphasia (receptive or expressive)
 - Apraxia
 - Altered level of consciousness
 - Impairment of cognitive skills
 - Motor weakness
 - Any change of grade ≥ 3 self-care activities of daily living
 - Any change identified by Patient or caregiver

Panel 3

Intervention

- Subject proximity (≤ 1 hr.) to a advanced medical center
- Pre-dose dexamethasone(20mg) will be given prior to initiation of blinatumomab at every cycle.

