4.1 Design

This study **aims** to determine the safety and feasibility of complete outpatient blinatumomab administration for subjects with MRD of B-precursor ALL using CWHMS to measure vital signs and transmit the vital signs to the HCP, mobile electronic devices (tablet) to electronically communicate with the HCP, and a Wi-Fi **and cellular** enabled platform for the transfer of data and communication between subject and HCP to detect clinically important changes. The data provided to the HCP will enable him/her to identify subjects at risk of developing grade 3 or 4 CRS, NT, or other SAEs requiring hospitalization during the MDMP. The HCP can then direct such subjects to the appropriate medical facility for hospitalization if needed.

During screening, subjects and caregivers will be trained on the CWHMS and assessed for compliance (Table 1-1-panel 1). Once enrolled, subjects will receive 2 complete cycles of blinatumomab in the outpatient setting in accordance with the monitoring and intervention guidelines (Table 1-1-panels 2 and 3).

After the end of cycle 2 clinical assessment visit, some subjects may continue to receive 2 additional (optional) cycles of outpatient blinatumomab. There will be no CWHMS outpatient monitoring during the optional cycles 3 and 4. For the purpose of this study, the MDMP is defined as the first 3 days of cycle 1 (72 hours) and the first 2 days of cycle 2 (48 hours) of blinatumomab infusion for subjects with MRD of B-precursor ALL.

The end of study visit will occur 30 days (+ 3 days) after the last dose of blinatumomab is administered (Figure 1-1).

This may coincide with the end of cycle 2 clinical assessment for subjects ending after cycle 2 or after cycle 3 or 4 if subjects and Pl's choose to receive the optional consolidation cycles 3 and/or 4.

The overall study design is described by a study schema in Section 1.2. The endpoints are defined in Section 3.

Date: 21 April 2022 Page 36 of 108

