6.1.3 Other Protocol-required Therapies

All other protocol-required therapies including dexamethasone, that are commercially available are not provided or reimbursed by Amgen (except if required by local regulation). The investigator will be responsible for obtaining supplies of these protocol-required therapies. Additional details regarding these protocol-required therapies are provided in the IPIM.

Dexamethasone Premedication

Premedication with dexamethasone (or prednisone) is required before each blinatumomab treatment cycle for prophylaxis of CRS. Dexamethasone 16mg (or equivalent prednisone 100 mg) should be given up to 6 hours prior to the start of blinatumomab infusion for each cycle. Dexamethasone will be the recommended steroid for this study. Subjects \geq 45 kg will have 2 additional 8mg doses (subjects < 45 kg will receive 2 doses of 5 mg/m² rounded to the nearest mg) of oral dexamethasone to use as needed for treatment of CRS symptoms only if instructed by HCP. It will be recommended that hospitalization be strongly considered for subjects who require interruption of blinatumomab for > 4 hours.

Date: 21 April 2022 Page 45 of 108

Intrathecal CNS Prophylaxis Before Treatment

Lumbar puncture and CSF analysis must be performed during screening to determine the presence of CSF lymphoblasts. Cerebrospinal fluid evaluation done as part of standard of care within 2 weeks of screening may be used. If CSF is positive, subjects must receive intrathecal chemotherapy as per site standard of care and a negative CSF must be documented prior to starting protocol-specified blinatumomab therapy. Subjects with persistent positive CSF will not be eligible. A repeat CSF on cycle 1 day 29 (prior to starting cycle 2 day 1) will be required only for subjects with positive CSF in screening.

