6.5 Drug Administration

The drug administration should not be interrupted, if possible. In case of infusion interruption, due to any technical or logistic reason, the interruption should be as short as possible, and the infusion restarted at the earliest time possible. Every interruption longer than 1 hour should be documented. Administration of dexamethasone premedication will occur as described in Section 6.1.3. If the infusion is interrupted, if possible, the total infusion time should equal 28 days in each cycle.

A dose of up to 10% higher than the intended blinatumomab dose (per day) may not require specific intervention. In case of overdose or medication error, the infusion should be immediately stopped. Routine supportive and symptomatic care according to standard medical practice is recommended. Once the subject is stabilized and no clinically relevant safety findings due to blinatumomab are observed, resumption of blinatumomab at a correct dose can be considered after consultation with the Amgen medical monitor.

For blinatumomab, a dose of greater than 10% higher than the intended dose will be considered clinically important and classified as a serious adverse event under the criterion of "other medically important serious event" per Section 11.4. If the overdose results in additional AEs, the subject should be followed carefully until all signs of toxicity are resolved and the AEs should be recorded/reported per Section 11.4 of the protocol.

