3.1 Study Design

This study **aims** to determine the safety and feasibility of complete outpatient blinatumomab administration for subjects with MRD of B-precursor ALL. The study will use the CWHMS that is comprised of **CH** wearable **device** worn on the **subject's** upper arm, **an** axillary temperature patch, a blood pressure cuff, a Wi-fi hub, tablet, **a** mobile phone **provisioned to the HCP**, and a platform will also be used to monitor subjects' vital signs while they are at home.

This study will include remote monitoring using CWHMS to measure vital signs and mobile electronic devices (tablet) to electronically communicate these vital signs with the HCP.

The use of a Wi-Fi **and cellular** enabled platform for the transfer of data and communication between subject and HCP, to identify subjects at risk of developing grade 3 or 4 CRS, NT, or other SAEs requiring hospitalization during the MDMP. This subject group may require immediate escalation of care and/or hospitalization once the digital monitoring system identifies changes.

Design

During screening, subjects and caregivers will be trained on the CWHMS and assessed for compliance (Table 1, panel 1). **Once enrolled,** Subjects will receive 2 **complete** cycles of blinatumomab completely in the outpatient setting in accordance with the monitoring and intervention guidelines (Table 1, panels 2 and 3).

After the end of cycle 2 clinical assessment visit, some subjects may continue to receive 2 additional (optional) cycles of outpatient blinatumomab. There will be no CWHMS outpatient monitoring during the optional cycles 3 and 4. For the purpose of this study, the MDMP is defined as the first 3 days of cycle 1 (72 hours) and the first 2 days of cycle 2 (48 hours) of blinatumomab infusion for subjects with MRD of B-precursor ALL.

The end of study visit will occur 30 days (\pm 3 days) after the last dose of blinatumomab is **administered (Figure 1)**.

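### Table 1-1 Panel 3 and its SAP copy give 20 mg dexamethasone premedication where the treatment text gives 16 mg; separately, the SAP drops the planned premedication exposure summary without declaring it

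*Protocol*

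**What the plan says.** **Dose.** Protocol Table 1-1 Panel 3 reads: "Pre-dose dexamethasone(20mg) will be given prior to initiation of blinatumomab at every cycle". SAP Appendix E carries the same line. The treatments part of the synopsis reads: "Dexamethasone 16 mg (or equivalent prednisone 100mg) intravenously (IV): up to 6 hours before start of treatment in each treatment cycle". Protocol Section 6.1.3 agrees with the synopsis: "Dexamethasone 16mg (or equivalent prednisone 100 mg) should be given up to 6 hours prior to the start of blinatumomab infusion for each cycle". Section 6.5, on drug administration, sends the reader there: "Administration of dexamethasone premedication will occur as described in Section 6.1.3".

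**Status of the table.** The synopsis says that the two outpatient cycles are given "in accordance with the monitoring and intervention guidelines (Table 1-1., panels 2 and 3"), and Section 4.1 repeats it: "in the outpatient setting in accordance with the monitoring and intervention guidelines (Table 1-1-panels 2 and 3"). SAP Section 3.1 points to the same panels in its own copy: "in accordance with the monitoring and intervention guidelines (Table 1, panels 2 and 3").

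**Exposure summary.** Protocol Section 9.4.2.3.6 plans descriptive statistics on exposure to the required dexamethasone premedication in the safety analysis set. SAP Section 9.6.10 has the same heading, and its only content is that the analysis is not applicable. SAP Section 10 lists the departures from the protocol: endpoint wording, the restriction of the resource-use endpoints to treatment-related events, and the replacement rule. It does not mention premedication.

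**The concern.** Section 6.1.3 makes the premedication a requirement before each cycle, as prophylaxis against CRS. Grade 3 or 4 CRS is a component of the primary endpoint, so this dose should have one value throughout the documents. As written, a site that follows Panel 3, as Section 4.1 directs, departs from Section 6.1.3. A site that follows Section 6.1.3 departs from Panel 3.

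The SAP omission is a separate defect. The protocol promises a summary that the SAP will not produce, and the section that exists to record such changes does not mention it. While two doses are in circulation, a premedication summary that included dose would also be the simplest way to show which one subjects received.

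**Working it through.** **1. Do the four dose statements concern the same thing?**

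| Place | Dose | When |
|---|---|---|
| Protocol Table 1-1 Panel 3 | dexamethasone 20 mg | every cycle |
| SAP Appendix E, Panel 3 | dexamethasone 20 mg | every cycle |
| Protocol synopsis, treatments | dexamethasone 16 mg or prednisone 100 mg | each cycle |
| Protocol Section 6.1.3 | dexamethasone 16 mg or prednisone 100 mg | each cycle |

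All four describe the dose before the start of infusion in each cycle. No text reconciles them by cycle, body weight or route. The 20 mg figure appears identically in both documents, so an error in reading one PDF is an unlikely explanation.

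**2. Size of the gap.**

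- Per dose: 20 − 16 = 4 mg; 4 / 16 = 25%.
- Cycles 1 and 2: 2 × 4 = 8 mg.
- Up to four cycles, if the every-cycle wording of Panel 3 is followed: 4 × 4 = 16 mg.

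**3. Which figure is better supported?** The two passages written to define the premedication both give 16 mg, and the drug-administration section refers to one of them. The 20 mg figure appears only in the monitoring table and its copy. The prednisone alternative of 100 mg is tied only to 16 mg (100 / 16 = 6.25 to 1); set against 20 mg it would imply a different ratio (100 / 20 = 5 to 1).

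**4. Does 20 mg break another rule?** Section 6.1.5 excludes systemic corticosteroids given for more than 7 days at more than 24 mg/day of dexamethasone or equivalent. A single 20 mg dose is below 24 mg/day and does not last more than 7 days, so the exclusion is not triggered.

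**5. Does any planned figure depend on the dose?** The only design figure is the expected upper 95% limit of 53.5% at n = 45 and p = 0.38. Averaging the exact (Clopper-Pearson) upper limit over the binomial distribution, Σ P(X = x) × U(x), gives 0.5352. At 17 events of 45 the upper limit is 0.5346. Both round to 53.5%, as stated, and premedication dose does not enter the calculation.

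**6. Is the planned summary produced elsewhere in the SAP?** SAP Section 9.6.11 counts subjects receiving concomitant medications by preferred term, without dose. The documents do not say on which form premedication is recorded. If it is recorded as a concomitant medication, the dexamethasone row would combine three uses: the premedication, the as-needed oral doses in Section 6.1.3, and the treatment doses for CRS and neurologic events in Table 6-2. That row would show neither who was premedicated nor at what dose. The protocol plans premedication exposure (9.4.2.3.6) and concomitant medication (9.4.2.3.7) as separate analyses.

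**The case against.** **The documents do not prove that 20 mg is the error.** This stands. Neither document has a precedence clause, Section 4.1 directs use of Panel 3, and Section 6.1.3 refers to the Investigational Product Instruction Manual for further detail, which is not available here. The case for 16 mg rests on two matching dose statements and the reference in Section 6.5. That is strong but not conclusive, so the sponsor should confirm the dose before the tables are changed.

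**A reader might infer that the discrepancy can only add prophylaxis, and so could lower the observed CRS rate.** The documents do not support this. The direction depends on which dose was intended: if it were 20 mg, sites following Section 6.1.3 would give too little. There is no dose-effect figure, and nothing shows that any site gave 20 mg.

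**A reader might take the training sentence in the synopsis as further evidence that the table sets the dose.** It says: "The HCP and the staff will also be trained on the infusion, usual side effects and response algorithm (Table 1-1"). But it concerns the response algorithm, which Panel 3 itself locates in Panel 2, not the premedication dose. The SAP does not instruct sites either. The table is operative because of the synopsis design text and Section 4.1 alone, which is enough.

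**A reader might count two dropped summaries, because SAP Section 9.6.9 on non-investigational product is also marked not applicable.** Only one was dropped. The protocol plans no separate analysis under that title, so Section 9.6.9 departs from nothing.

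**The loss may be smaller than it looks.** Section 9.4.2.3.6 does not mention dose, and the SAP's concomitant-medication table is wider than the protocol's, which covers only therapies of interest. If premedication is on that form, recipients of dexamethasone would be counted. Also, SAP Section 9.6.10 states openly that it is not applicable. These points limit the weight of the omission. They do not make a pooled preferred-term count equivalent to the planned summary, and they do not supply the missing entry in Section 10.

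**Conclusion.** Both mismatches are certain on the current text, and both are minor. The first is a conflict of 4 mg (25% of 16 mg) in an operative dosing instruction for required CRS prophylaxis, with 16 mg the better-supported figure. The second is one protocol-planned descriptive summary removed from the SAP without being declared in Section 10. How much information is lost depends on how premedication is recorded, which the documents do not state.

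The conclusion assumes only that the four dose statements refer to the same premedication, which their wording supports. It does not extend to bias in the primary endpoint: no effect on the primary rate, the sample size or the confidence interval is shown.

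**What to change.** **Dose.** The sponsor confirms that 16 mg is intended and checks that the instruction manual agrees. Table 1-1 Panel 3 and SAP Appendix E are then corrected to 16 mg or equivalent prednisone 100 mg, and sites are notified. Cost: one line in each table and a site memo.

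**Summary.** Either restore in SAP Section 9.6.10 a simple descriptive table of premedication exposure in the safety analysis set, including dose if it is recorded, or add a row to SAP Section 10 that declares and justifies the removal. Cost: one table or one row. If premedication is recorded with concomitant therapies, Section 6.6.2 already requires dose and indication, so no new data collection would be needed.
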